# Research question and objectives

#### **Research question:**

What is the safety profile and clinical effectiveness of rapidly infused CT-P10 in patients with non-Hodgkin's lymphoma (NHL) or chronic lymphocytic leukaemia (CLL) in the real world clinical setting?

#### **Hypothesis:**

This is a descriptive study and there is no *a* priori hypothesis to be tested.

#### **Primary research objective:**

To describe the incidence of infusion-related reactions (IRR) associated with rapid infusion of CT-P10 in patients with NHL or CLL on day 1 or day 2 after the index event (index event defined as the first rapid infusion of CT-P10, which must have been given as part of the second or a subsequent treatment cycle).

#### Secondary research objectives:

To describe the following in patients who receive rapid infusion of CT-P10 for the treatment of NHL or CLL:

- 1. Safety profile in the 6 months post-index date (index date defined as the date of the first rapid infusion of CT-P10, which must have been given as part of the second or a subsequent treatment cycle), including incidence (and frequency per patient per month, where appropriate) of the following safety events: IRRs, grade 3 or grade 4 IRRs, any adverse event (AE), any serious adverse event (SAE), any grade 3 or grade 4 AE, AEs as the primary cause for treatment discontinuation.
- 2. Clinical effectiveness in the 6 months postindex date (to be analysed separately for NHL and CLL), including overall survival (OS), progression free survival (PFS), best response, overall (complete/partial) response rate, time to complete or partial response.

	
 
NHL / CLL treatment patterns during the observation period (from diagnosis of NHL or CLL to 6 months post-index date), including types and doses of treatment, number and duration of infusions, time on treatment and reasons for discontinuation.
 
Patients' demographic, clinical, and NHL/ CLL disease characteristics.
 

Country(-ies) of study	UK, Spain, France, Italy and the Netherlands.
Author	[name] RPh., MScMed. Celltrion Healthcare Co., Ltd.  [name] BSc. [name] Ph.D. pH Associates Ltd.

# 2. List of abbreviations and key definitions

# 2.1 List of abbreviations

Abbreviation	Definition					
ABPI	Association of the British Pharmaceutical Industry					
AE	Adverse event					
ASH	American Society of Hematology					
CFR	Code of Federal Regulations					
CI	Confidence interval					
CLL	Chronic lymphocytic leukaemia					
DLBCL	Diffuse large B-cell lymphoma					
DMP	Data management plan					
EDC	Electronic data capture					
eDCF	Electronic data collection form					
EHA	European Hematology Association					
EMA	European Medicines Agency					
ENCePP	European Network of Centres for Pharmacoepidemiology					
	and Pharmacovigilance					
FDA	Food and Drug Administration					
FL	Follicular lymphoma					
FLIPI	Follicular Lymphoma International Prognostic Index					
GCP	Good Clinical Practice					
GDPR	General Data Protection Regulation					
GPP	Guidelines for Good Pharmacoepidemiology Practices					
IEC	Independent Ethics Committee					
IPI	International Prognostic Index					
IRB	Institutional Review Board					
IQR	Interquartile range					
IRR	Infusion-related reaction					
ISPE	International Society for Pharmacoepidemiology					
IWCLL	International Workshop on Chronic Lymphocytic					
	Leukaemia					
LDH	Lactate dehydrogenase					
NHL	Non-Hodgkin's lymphoma					
PASS	Post-authorisation safety study					
R&D	Research and Development					
SAE	Serious adverse event					
SAP	Statistical analysis plan					
SD	Standard deviation					
SOP	Standard operating procedure					
UK	United Kingdom					

## 2.2 Key definitions

- **Index event:** first rapid infusion of CT-P10 (note: first rapid infusion must have been given as part of the second or a subsequent treatment cycle).
- **Index date:** date of first rapid infusion of CT-P10 (note: first rapid infusion must have been given as part of the second or a subsequent treatment cycle) (day 1).
- **Rapid infusion:** defined as a total infusion time for CT-P10 of 90 minutes or less.
- **Infusion-related reaction (IRR):** any adverse event (AE) from a pre-defined list (see Annex 3) occurring on day 1 or day 2 after an infusion of CT-P10.
- Pre-index observation period: the pre-index observation period for this study
  will be from the date of diagnosis of NHL or CLL until the index date, and will be
  used to capture patients' demographic and clinical characteristics.
- Post-index observation period: patients will be observed for a period of 6
  months after the index date (or until death, if sooner), to capture safety and
  clinical outcomes.
- Adverse event (AE): An AE is any untoward medical occurrence in a patient administered a pharmaceutical product and which does not necessarily have to have a causal relationship with this treatment. An AE can therefore be any unfavourable and unintended sign (including an abnormal laboratory finding, for example), symptom, or disease temporally associated with the use of a medicinal product, whether or not considered related to the medicinal product. The definition of an AE includes worsening of a pre-existing medical condition.

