## 9.2 Setting

#### 9.2.1 Study population

The source population for this study is adult patients with NHL or CLL who received treatment with rapidly infused CT-P10 as part of their standard clinical care in five European countries.

Patients fulfilling the following criteria will be potentially eligible for inclusion in the study:

- Patients with a confirmed diagnosis of NHL (follicular lymphoma [FL] or diffuse large B-cell lymphoma [DLBCL]) or CLL.
- Patients who had received rapidly infused CT-P10 for their second or a subsequent treatment cycle; 'rapidly' defined as 90-minutes or less.
- Patients at least 18 years of age at the date of diagnosis of NHL or CLL.
- Patients (or next of kin, if appropriate locally) providing written informed consent for study data collection (if this is required according to local country regulations).

Patients fulfilling any of the following criteria will be excluded from the study:

- Patients who had received reference rituximab for any previous treatment cycles
   (i.e. prior to the index event) within the same line of treatment.
- Patients whose medical records are unavailable for review.

As only limited exclusion criteria will be applied, and patients will be included from a range of centres in five European countries, it is expected that the study population will be representative of the overall source population.

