# Endpoint to address the primary objective

# Variables required to address the primary objective

Primary objective: To describe the incidence of IRR associated with rapid infusion of CT-P10 in patients with NHL or CLL on day 1 or day 2 after the index event (index event defined as the first rapid infusion of CT-P10, which must have been given as part of the second or a subsequent treatment cycle).

Proportion of patients who experience an IRR\* on day 1 or day 2 after the index event.

- Did IRR(s) occur on day 1 or day 2 after the index event (Yes/No)?
- \* An IRR is defined as any AE from a predefined list (see Annex 3) occurring on day 1 or day 2 after an infusion of CT-P10.
- If yes, IRR description and date

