# Endpoint to address the secondary objective

# Variables required to address the secondary objective

Secondary objective 1: To describe the safety profile of rapidly infused CT-P10 in patients with NHL or CLL in the 6 months post-index date

- Proportion of patients who experience the following safety events in the 6 months post-index date, and frequency of each per patient per month:
  - Any IRR.
  - Any grade 3 or grade 4 IRR (according to the Common Terminology Criteria for Adverse Events [CTCAE] version 4).
  - Any other AE (excluding IRR).
  - Any other grade 3 or grade 4 AE (excluding IRR).
  - o Any serious adverse event (SAE).
- Proportion of patients with AEs as the primary cause for treatment discontinuation.
- Summary distributions of event type by grade.
- Proportion of all rapid CT-P10 infusions during which IRRs were experienced.

For all AEs (temporally associated with CT-P10 treatment) during the 6 months post-index (including the index date):

- Description of AE
- IRR (Yes/No)
- Event start date
- Event end date
- Seriousness
- CTCAE v4.0 grade
- Clinician's assessment of relationship to CT-P10
- AE resulted in treatment discontinuation (Yes/No).

Secondary objective 2: To describe the clinical effectiveness of rapidly infused CT-P10 in patients with NHL or CLL in the 6 months post-index

- OS, defined as the time from the index date until death from any cause.
- Proportion of patients surviving at six months following NHL or CLL diagnosis and following the index date.
- PFS, defined as the time from the index date until the first documented evidence of disease progression or death from any cause.
- Proportion of patients surviving and free from disease progression at six months following the index date.
- Summary of best response to CT-P10

- Date of data collection.
- Patient alive at 6 months post-index (Yes / No / Not known)?
- If no, date of death (DD/MM/YYYY).
- All treatment response assessments in the post-index period (date, recorded treatment response [complete response / partial response / no response or stable disease / progressive disease], assessment based on IWCLL / Revised Response Criteria for Malignant Lymphoma / local criteria / other criteria, type(s) of

- (complete response / partial response / no response or stable disease / progressive disease).
- Proportion of patients achieving a complete or partial response.

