#### 9.7.4 Subgroup and sensitivity analyses

Subgroup analyses may be conducted to further evaluate the safety and clinical effectiveness of CT-P10 in patients with NHL or CLL. This may include, but will not be limited to:

- Diagnosis (NHL [further stratified by FL / DLBCL] / CLL).
- Infusion time for the index event (90 minutes, 60<90 minutes, <60 minutes).
- Patients with / without prior exposure to a rituximab-containing regimen.

No sensitivity analyses are planned.

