#### 9.9 Limitations of the research methods

- Patient or next of kin consent may be a requirement for this study in some of the participating countries; this may introduce selection bias, resulting in a study sample that may not be representative of the wider patient population of
- **Thterest**erpretation of data collected retrospectively will be dependent on the completeness and quality of the medical records and the reliability of the abstraction of data from the medical records.
- The primary endpoint of this study is the incidence of IRR on day 1 or day 2 after the index event. It is expected (based on scoping interviews) that IRRs occurring during or shortly after the CT-P10 infusion should be reliably documented in

patients' infusion records, however, it is possible that IRRs occurring the day after the infusion may be less well-documented. This may result in an underestimate of the overall incidence of IRR during the observation period, particularly of milder events. The IRR rate may also be underestimated as a result of the definition of a rapid infusion as 90 minutes or less, since this may result in the exclusion of cases where the initial intention was to infuse CT-P10 over 90 minutes, but the infusion was delayed or stopped due to IRRs.

- The patient records included in this study will be from physicians and study sites
  that are willing to participate. Therefore, study findings may not be generalisable
  to all patients with NHL or CLL treated with rapid infusion of CT-P10 or to all
  physicians who treat these patients in the participating countries.
- As this is a non-interventional study conducted in a routine clinical practice setting, the assessment of treatment response may not be uniform, particularly with regard to the timing of evaluations. In particular, it is likely that disease progression for the identified patients will have been monitored at less frequent intervals than would be required in a clinical trial and therefore progression events will be identified later. This may result in upwardly biased estimates of PFS. For this reason, any findings regarding the endpoints of clinical response should be considered to be 'real world estimates' which may not be directly comparable to those observed in clinical trials.
- This is a descriptive study and no adjustments to control for confounding will be carried out.

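### Rapid infusion is defined by the time the infusion actually took, so a reaction that slows the infusion past 90 minutes can remove its own event from the primary IRR rate

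*Protocol*

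**What the plan says.** Protocol section 2.2 has rapid infusion "defined as a total infusion time for CT-P10 of 90 minutes or less", with no reference to planned or prescribed time. Four other parts of the plan rest on that definition:

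- **Eligibility** (section 9.2.1): "Patients who had received rapidly infused CT-P10 for their second or a subsequent treatment cycle; 'rapidly' defined as 90-minutes or less".
- **Index event** (section 2.2): the first infusion in cycle 2 or later that meets the definition.
- **Primary endpoint** (section 9.3): "Proportion of patients who experience an IRR\* on day 1 or day 2 after the index event". Its denominator is the patients so indexed.
- **Per-infusion secondary endpoint** (section 9.3, secondary objective 1): "Proportion of all rapid CT-P10 infusions during which IRRs were experienced".

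The optional subgroups in section 9.7.4 also use infusion time: "Infusion time for the index event (90 minutes, 60<90 minutes, <60 minutes".

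Section 9.9 recognises the consequence. It says the IRR rate may be underestimated because the definition may exclude cases where "the initial intention was to infuse CT-P10 over 90 minutes, but the infusion was delayed or stopped due to IRRs". Section 9.7.4 nevertheless states: "No sensitivity analyses are planned". The variables in section 9.3 include the duration of each infusion but no planned duration, and no field for slowing or stopping because of a reaction. Section 9.7.1 compares the resulting rate by Z-test with published reference rituximab rates.

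**The concern.** The time an infusion takes depends partly on whether the patient reacts. Classifying exposure by that time selects patients on a consequence of the outcome, in two ways.

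- A patient whose only intended rapid infusion overran because of an IRR never qualifies, and the event is not seen.
- A patient whose first intended rapid infusion overran, but who later completed one in time, is indexed at the later infusion. The reaction is then reported among baseline characteristics (section 9.3, secondary objective 4) and not in the primary endpoint.

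In the optional subgroups, an infusion planned for a shorter band but prolonged by a reaction moves to a slower band.

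The study's single primary figure is the IRR rate with rapid infusion. A downward shift caused by the definition would read as a better safety profile, and a larger sample would not reduce it.

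**Working it through.** **Inputs.** From section 9.5: N = 300, planning rate 10%, expected 95% CI 6.8% to 14.0%, published rate 8.84%. Assumed, because the protocol gives neither: q, the share of IRR infusions pushed past 90 minutes, and r, the share of non-IRR infusions that overrun for other reasons.

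**Step 1: the plan's own figure.** The exact (Clopper-Pearson) interval for 30/300 is 6.8% to 14.0%, as stated. The half-width is 7.2/2 = 3.6 points.

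**Step 2: observed rate.** Let p be the true rate among all infusions intended to be rapid. Among those that finish within 90 minutes,

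observed = p(1−q) / [p(1−q) + (1−p)(1−r)].

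For p = 10%:

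| q | r = 0 | r = 10% |
|---|---|---|
| 10% | 0.090/0.990 = 9.1% | 0.090/0.900 = 10.0% |
| 25% | 0.075/0.975 = 7.7% | 0.075/0.885 = 8.5% |
| 50% | 0.050/0.950 = 5.3% | 0.050/0.860 = 5.8% |

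The bias is downward when q exceeds r and vanishes when q = r.

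**Step 3: comparison with the planned precision (r = 0).** The shortfall is 0.9 points at q = 10%, 2.3 at 25% and 4.7 at 50%. Setting the observed rate to 10% − 3.6 = 6.4% gives q = 0.036/0.0936, about 38%, so the bias passes the half-width only from there. From about q = 37% the expected exact interval at N = 300 no longer contains 10%.

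**Step 4: re-entry at a later infusion.** Take 300 patients with 30 IRRs at the first intended rapid infusion. Suppose every patient whose infusion overran is indexed later, with a 10% risk at that infusion.

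- q = 25%: (22.5 + 0.75)/300 = 7.75%.
- q = 50%: (15 + 1.5)/300 = 5.5%.

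Re-entry does not remove the bias.

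**Step 5: the external comparison.** As an illustration, treat 8.84% as a fixed comparator and suppose the true rate here is also 8.84%, with r = 0. The standard error is √(0.0884 × 0.9116/300) = 1.64 points.

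- q = 25%: observed 0.0663/0.9779 = 6.8%, z about −1.3.
- q = 50%: observed 0.0442/0.9558 = 4.6%, z about −2.6, p about 0.01.

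**Step 6: stopped infusions.** Section 2.2 read literally keeps any infusion abandoned for good within 90 minutes, including one started at the standard rate. Section 9.9 lists stopped infusions among those that may be excluded. The two do not agree, and nothing says whether pauses count towards total time. Retained standard-rate infusions stopped for an IRR would push the rate upward. That effect is not in the figures above.

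**The case against.** The protocol discloses this bias and its direction, and the study is declared descriptive. The overrun share is unknown, and several features argue against a high value for the all-grade rate. Section 7 calls IRRs usually mild to moderate and puts peak onset at 30 to 120 minutes, so some begin near or after the end of a 90-minute infusion. The IRR window includes day 2, when a reaction can no longer lengthen the infusion. Annex 3 counts items such as nausea, fatigue and headache, which need not slow it. At overrun shares of 10% or 25% the bias stays inside the planned precision. IRRs before the index event are still recorded, with date, duration and grade, for patients who later qualify. Finally, nothing shows that planned time can be found in retrospective records.

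All of this limits the size and calls for a fallback in the remedy. It does not remove the selection. Disclosure is not correction, and a later analysis plan cannot recover patients who were never enrolled or fields that were never collected.

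A reader might infer that the grade 3/4 rate is especially biased. The documents do not support that. The six-month any-IRR and grade 3/4 endpoints count reactions after any CT-P10 infusion in the post-index period, however long it took, so the definition touches them only through who is indexed and when. Reactions severe enough to end an infusion within 90 minutes literally stay in. A reader might also infer that every slowed or stopped infusion is lost. Step 6 and the recorded pre-index IRRs show otherwise.

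**Conclusion.** The point holds for the primary endpoint and the per-infusion IRR endpoint. Exposure is defined partly by a consequence of the outcome, and the plan concedes the resulting underestimation without collecting the data or planning the analysis that would correct or bound it. The bias is downward provided IRR infusions overrun more often than other infusions, which is the mechanism section 9.9 describes.

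Its size cannot be derived from the protocol. The illustrations run from no bias (10% of both kinds of infusion overrun) to an observed 5.3% for a true 10% (half of IRR infusions overrun and no others). They leave out infusions abandoned within 90 minutes, on which sections 2.2 and 9.9 must be reconciled. The Z-test illustration also assumes that the published rate is free of the same selection, which the protocol does not establish.

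**What to change.** **Main change.** Define the index event as the first CT-P10 infusion in cycle 2 or later that was planned or prescribed to run in 90 minutes or less, whatever time was achieved. Align the eligibility criterion with it. Take planned time from the chart or prescription, or from the site's rapid-infusion protocol where the record is silent.

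- Add eDCF fields for planned duration and for slowed, interrupted or stopped because of a reaction.
- State how paused and stopped infusions are timed, and reconcile sections 2.2 and 9.9.
- Use planned time for the per-infusion denominator and any infusion-time subgroups.
- Keep achieved time of 90 minutes or less as a sensitivity analysis.

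**Fallback.** Use the pilot in section 9.8 to check whether planned time is available. If it is not, keep the current definition, but also collect patients whose cycle-2-or-later infusion exceeded 90 minutes with a documented IRR or interruption. Add a sensitivity analysis that includes those infusions.

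**Cost.** Protocol wording and a few eDCF fields, cheap if made before data collection starts. Some planned times will have to be inferred from site policy, which may misclassify patients deliberately given a standard-rate infusion. The reported IRR rate may be less favourable. The change concerns classification of records only and does not affect patient care.

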#### • **Serious adverse event (SAE):** a SAE is an AE that:

- is fatal
- o is life threatening (places the subject at immediate risk of death)
- o requires in-patient hospitalisation or prolongation of existing hospitalisation
- results in persistent or significant disability/incapacity
- o is a congenital anomaly/birth defect
- other significant medical hazard.

- **Adverse event grade:** AEs will be defined as grade 1, 2, 3, 4 or 5 according to the Common Terminology Criteria for Adverse Events v4.0 (CTCAE).
- **Overall survival (OS):** defined as the time from the index date to death from any cause.
- **Progression free survival (PFS):** defined as the time from the index date to the first documented evidence of disease progression or death from any cause. The assessment of disease progression will be based on the International Workshop on Chronic Lymphocytic Leukemia (IWCLL) criteria for CLL or the Revised Response Criteria for Malignant Lymphoma for NHL, if these criteria are used and documented locally. If different criteria are used in routine practice, disease progression will be defined as documented in the medical records.
- Complete response (CR) or partial response (PR): will be based on IWCLL criteria for CLL or the Revised Response Criteria for Malignant Lymphoma for NHL, if these criteria are used and documented locally. If different criteria are used in routine practice, response will be defined as documented in the medical records.

#### 4. Abstract

#### **Title**

The safety and clinical effectiveness of rapid infusion with CT-P10 in patients with non-Hodgkin's lymphoma or chronic lymphocytic leukaemia: a retrospective non-interventional post-authorisation safety study in Europe

#### **Protocol version**

2.0

#### Date of last version of protocol

18 April 2018

#### Rationale and background

In February 2017, CT-P10 became the first biosimilar version of rituximab to be approved by the European Medicines Agency (EMA) for the treatment of rheumatic diseases and specific blood cancers including non-Hodgkin's lymphoma (NHL) and chronic lymphocytic leukaemia (CLL).

The safety profile of rituximab has been documented in numerous clinical trials, with infusion-related reactions (IRRs), thought to be related to the release of cytokines, being the most commonly reported adverse reaction. To minimise the risk of IRRs, the standard administration protocol for rituximab, specified in the summary of product characteristics, takes approximately three to four hours for the first infusion and two to three hours for subsequent infusions for oncology treatment. This standard infusion protocol places a significant burden on the healthcare system and patients and, consequently, many healthcare professionals now administer rituximab as a rapid infusion (over a period of 90 minutes or less) for second or subsequent infusions in patients who did not experience serious complications with their initial infusion(s).

A number of studies have been conducted to evaluate the safety of rapid infusion of rituximab in patients with haematological malignancies and have generally shown rapid administration to be safe and well-tolerated, with low incidences of  $IRRs^{9,11-14}$ . However, there are very limited data available on the safety of rapid infusion of  $CT-P10^{15}$ . These data are important to inform future decisions by physicians and healthcare providers regarding the most appropriate and cost-effective treatment strategy.

This study will address this evidence gap by collecting real world data on the safety and effectiveness of rapidly infused CT-P10 in patients with NHL and CLL in Europe.

